8. QUALITY ASSURANCE AND QUALITY CONTROL

The investigative team understands the critical importance of collecting complete, high-quality data and developing procedures to accomplish this important objective. Core activities include:

- Standardization - maintaining common study documents (protocol, MOP, case report forms) with special efforts to minimize version control issues.
- Training – developing training procedures led by experienced investigators and senior staff, developing and implementing certification procedures and performance metrics, and conducting annual training.
- Robust data systems – implementing a web-based data entry system with duplicate data entry; using off-site data storage with automated back-up systems; programming data queries to check logic and consistency of data between forms over time; implementing replicate programming for major papers.
- Site visits – conducting site visits has an important role in promoting best practices, identifying operational problems not evident in trial reports, and maintaining a culture that promotes high quality.
- Performance monitoring with feedback – tracking enrollment and follow-up (observed/expected, overall and by key subgroups); monitoring missed visits, data completeness, protocol deviations, and data entry errors; distributing feedback through routine trial monitoring reports. These reports, together with constructive feedback, have an important role in identifying and resolving issues expeditiously.

9. RANDOMIZATION AND MASKING

Randomization

A variable 2, 4, or 6 block randomization scheme will be generated the Johns Hopkins University Institute of Clinical and Translational Research. The scheme will entail two orders AB or BA consistent with our crossover design. Details of the block sizes will be concealed from study staff and investigators and generated prior to the study and placed in opaque, sealed envelopes. A designated staff member will open the envelope with the participant during the randomization visit after confirmation of eligibility and informed consent. This will be performed in a private location away from other staff. Once assigned order is revealed, this information will be shared with the study dietitian, who will provide instructions pertinent for each intervention phase. Order of intervention will not be shared with research technicians performing data assessments or with study investigators. Study personnel and investigators will not be unmasked until follow-up and all data collection are completed.

10. INTERVENTIONS

Distribution and adherence

Overview: The intervention groups are summarized below. Participants will complete each of the study periods in random order. Participants will be asked not to start diuretics or ULD during the trial period (i.e., 10-12 weeks from SV1 to FP2).

Self-Directed (SD): The SD group was asked to continue their typical routine for grocery shopping and meal preparation.

Dietitian-Directed Tailored DASH diet (DD) Group: The DD intervention will consist of a one-on-one session with a dietitian at baseline, followed by weekly calls and assistance with food purchases. After the initial one hour visit, the dietitian will meet with the participant by phone every week to order next week's groceries. Participants will be allotted a stipend of \$105/week for the purchase of food (i.e. \$15/day). We will work with AmazonFresh to order and deliver foods to the ProHealth research center for weekly pick-up. Food will be ordered in fixed proportions reflecting the DASH diet:⁶ 4 servings/day of fruit, 3-4 servings/day of vegetables, 1-2 servings/day of lean meat (poultry/fish), 1-2 servings/day of low fat dairy, and 1-2 servings/day of high fiber foods (nuts, beans). During the intervention period participants will be asked to restrict alcohol, sugary beverages (no soda, no juice), red meat, shellfish, organ meats, and sweets. Food orders will be selected to be low fat, low saturated fat, and low cholesterol with a sodium target of <2300 mg per day. Little education will be provided during the DASH grocery intervention to minimize carryover effects. Rather, education will be focused on how to consume diet per the trial protocol.

Orders will target the following weekly servings with an emphasis on fruit/vegetables/dairy if budget constraints:

- i. Grain: 36-49 servings (5-7/d)
- ii. Vegetables: 28 servings (4/d)
- iii. Fruit: 28 servings (4/d)
- iv. Low fat/fat free dairy: 14 servings (2/d)
- v. Lean animal protein: 9-14 servings (1-2/d)
- vi. Nuts/Seeds/Legumes: 2 servings (<0.5/d)
- vii. Fats/oils/spices: not applicable; use over week

Monitoring Adherence

For all participants, adherence to dietary changes will be assessed by the Fruit, Vegetable, and Fat Screener questionnaire: a self-reported and validated measure of daily fruit and vegetable intake.¹² Respondents are asked about how often they ate a variety of fruits and vegetables over the past month. They are also asked to indicate portion size for each fruit or vegetable item that they ate. Objective measures of adherence will be urine potassium and sodium excretion. The brief screeners have been found to be a useful tool for monitoring diet and correlates well ($r=0.6$ to 0.7 , $P<0.0001$) with the Block full length food frequency questionnaire.

11. SAFETY

Safety monitoring

The study will monitor participant safety. One aspect of safety monitoring is to evaluate screenees to determine whether it is safe for them to participate. Key safety related eligibility criteria are the exclusion of persons with baseline hyperkalemia or chronic kidney disease as the DASH diet is a higher potassium diet.

In addition, while risk from the diet is anticipated to be minimal we will be obtaining clinical data, specifically blood pressure and lab values, and it is possible to detect abnormal clinical values unrelated to the study. All labs will be reviewed by a study physician. Any critically abnormal values will be communicated immediately to participants and permission will be obtained to communicate directly with their primary care provider (PCP). Values that are mildly abnormal will be communicated via letter with encouragement to follow-up with their PCP. With regards to blood pressure, if systolic blood pressure is >180 mm Hg or diastolic blood pressure is >110 mm Hg, we will notify the study physician and advise the participant to follow-up with their primary care provider within 7 days. If systolic blood pressure is >160, but ≤180 mm Hg or if diastolic blood pressure is >100, but ≤110 mm Hg we will advise participants to follow up with primary care provider within 1 month.

We will also monitor participants for gout flares (a health condition related to our intervention) and for medical conditions unrelated to our intervention. If a participant develops a medical problem this will be reviewed by the study physician and discussed with the participant's PCP.

Our study will have a designated study clinician who will review medical eligibility criteria, clinical measures, and laboratory reports. This individual will also serve as the primary contact for staff, participants, and their PCPs regarding medical issues.

The study clinician will also be responsible for reviewing and reporting any adverse events for the site. This person or persons will have appropriate back-up during vacations or other absences to provide 24/7 medical safety coverage for the duration of the study.

Potential risks

This study should not involve any major risk to screenees and trial participants. However, there are some potential risks associated with participation in this study, which are as follows:

1. Participants may be uncomfortable with certain questions on the questionnaires.
2. Bruising and a rare chance of local infection from venipuncture to collect blood samples could occur.
3. There might be loss of confidentiality and privacy.
4. Change in uric acid levels could precipitate a gout flare

Adverse event surveillance and reporting procedures

The OHRP defines an adverse event as “Any untoward or unfavorable medical occurrence in a human subject, including any abnormal sign, symptom, or disease, temporally associated with the subject's participation in the research, whether or not considered related to the subject's participation in the research.”

We will monitor for adverse and other relevant clinical events associated with study participation during in-person visits. In addition, it is possible participants may report events during grocery ordering calls (phone contact). A study clinician will review completed forms and labels and take appropriate action for any abnormal clinical values or reports of medical conditions. Serious events thought to be secondary to the study intervention will be reviewed by the investigative team of 4 physicians, during our weekly trial meeting.

The trial operation will be organized into teams of investigators and staff. The primary decision making body for the trial operation will be the Oversight Committee, chaired by the PIs ([name] and [name]) and comprised of all investigators and senior staff. This committee will convene monthly, review the progress of all components, and focus on high-level scientific and administrative issues.

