4. OVERVIEW OF DESIGN

This study will be an individual level, crossover RCT with 2 periods (**Figure**). The participants will be 40 adults with gout and hyperuricemia (≥ 18 years) who have SUA ≥ 7 mg/dL, who are not currently taking ULD. After informed consent, screening, and run-in, participants will be randomly assigned to each of two groups in random order: 1) Self-Directed (SD) vs. 2) DietitianDirected DASH Tailored (DD) with the provision of food. The primary outcome variable is SUA.

The duration of the intervention will be 4 weeks. Two screening visits will be used to determine interest and eligibility. The rationale for this timeline is that it is of sufficient duration to allow a complete effect of the intervention on uric acid to occur. Because it is not a prolonged period of intervention, the risk of non-compliance will be reduced, allowing for a better determination of the efficacy of the intervention. The DASH diet effects on SUA occur within 4 weeks and on blood pressure occur within 2 weeks, and are sustained from 2 weeks forward. As such, the 4 weeks will also provide sufficient time to see maximum diet effects on SUA and blood pressure and reduce the time period where recidivism is likely to occur.

Protocol visits for in-person data collection will occur during the screening period, at randomization, at week 4 after follow-up period 1 and follow-up period 2. At all protocol visits, our blinded data collectors will collect blood pressure and study questionnaires from participants in both arms of the study. Blood collection will be performed by phlebotomists blinded to the intervention arm.

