Feeding Period 2 Visit (FP2) – This in-person visit includes diet screening, a medication questionnaire, a physical activity questionnaire, a pain assessment, a questionnaire about adverse effects from diet, compliance, and palatability. In addition, we will perform phlebotomy, urine assessments, and physical examinations including weight, BP, OH, and the TUG test. We will also provide participants with some close-out materials including a certificate of appreciation.

Table. Data Collection Schedule

	Pre-	Screening/Baseline/Randomization			Feeding Periods Period	
	screen PSV	SV1	SV2	RZ	FP1	FP2/Close-out
Pre-screen questionnaire	✓					
Study description/instructions	✓	✓		✓		
Informed consent		✓				
Randomization assignment				✓		
Eligibility checklist		✓	✓			
Medication list questionnaire		✓	✓	✓	✓	✓
Medical history		✓				
Demographic questionnaire			✓			
Physical activity questionnaire (for Calorie estimator)			✓	✓	✓	✓
Gout questionnaire			✓			
Global pain and function questionnaire			✓		✓	✓
Diet compliance					✓	✓
Diet palatability/Symptom/diet tolerance questionnaire (DD intervention only)					✓	✓
Interim event			✓	✓	✓	✓
Diet screener (fruit/vegetables/fat)			✓		✓	✓
Serum collection		✓			✓	✓
Urine collection		✓			✓	✓
Seated blood pressure			✓	✓	✓	✓
Orthostatic hypotension			✓	✓	✓	✓
Height			✓			
Weight			✓	✓	✓	✓

TUG test			✓		✓	✓
Close-out survey with certificate						✓

Note: During the DASH intervention, participants will complete weekly food ordering calls with the study dietitian. Grocery orders will be documented.

Measurements

Primary outcome variable.

Uric acid. Fasting blood will be collected during SV1, FP1, and FP2 for SUA, blood glucose, total cholesterol (TC), HDL cholesterol (HDL-C), and triglycerides. LDL-C will be estimated by the equation (LDL=TC-HDL-triglyceride/5).

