- Rigorous training of clinic staff emphasizing the importance of:
 - Positive and warm interpersonal relationships between the participants and study staff
 - Study commitment during the consent process to ensure that potential participants understand the importance of completing the study
 - Addressing participant concerns to minimize dissatisfaction
 - Collecting data even if a participant discontinues the study treatment

Reasons for any drop-outs will be documented. If a drop-out occurs for reasons related to the study, i.e., informative censoring, we will perform sensitivity analyses using established methods for addressing informative censoring, namely, imputation techniques for missing data, best and worst-case scenarios, and use of the drop out event as a study end-point.⁹ We will review these approaches to minimize bias. Further, we will compare the baseline characteristics of participants with missing measures between the two assignments.

6 Safety outcomes

We will compare the rate of gout flares by assignment group using Poisson regression. We will also compare self-reported symptoms that are thought to potentially arise from the diets.

7 References

2. Senn SS. *Cross-over Trials in Clinical Research*. Second. John Wiley & Sons, Ltd; 2002.

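### The comparison of gout flares and self-reported symptoms between diets can be biased against DASH, because the DASH phase has event-reporting routes that the self-directed phase lacks and the SAP does not fix the source of counted events

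*Protocol*

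**What the plan says.** **Event capture.** Protocol section 11 makes visits the planned route: "We will monitor for adverse and other relevant clinical events associated with study participation during in-person visits". It then names a second one: "it is possible participants may report events during grocery ordering calls (phone contact".

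**Contact on DASH.** The note under the schedule in Protocol section 7 says: "During the DASH intervention, participants will complete weekly food ordering calls with the study dietitian". Section 10 agrees that "the dietitian will meet with the participant by phone every week", and adds a weekly trip to the research unit, since the study will "order and deliver foods to the ProHealth research center for weekly pick-up".

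**Contact on the self-directed (SD) diet.** Section 10 says only: "The SD group was asked to continue their typical routine for grocery shopping and meal preparation". No call or visit is scheduled between the start and the end of that phase.

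**Forms.** In the section 7 schedule, the Interim event row is ticked at FP1 and FP2, so once at the end of each phase whatever the diet. The palatability, symptom and tolerance questionnaire is marked as DD (DASH) only. The gout questionnaire is ticked at SV2 only.

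**Analysis.** SAP section 6: "We will compare the rate of gout flares by assignment group using Poisson regression". It also plans a comparison of self-reported symptoms that the diets might cause. It names no data source for either and gives no rule for events first reported on a call.

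**The concern.** The same person is observed more closely on one diet than on the other. A short or mild flare early in the DASH phase can be mentioned on the next weekly call. The same flare early in the SD phase has to be remembered at the end-of-phase visit, unless the participant contacts the study unprompted. If call reports are counted, the flare rate on DASH rises relative to SD with no effect of diet.

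Randomizing the order does not help. In both sequences the calls accompany DASH, so a within-person comparison keeps the whole asymmetry. Calls are also taken by the dietitian, who knows the assigned order, whereas Protocol section 9 withholds it from the technicians doing assessments.

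Flares matter here. Protocol section 11 lists a flare brought on by a change in uric acid as a risk of taking part, and SAP section 1.2 includes flares in aim G. An apparent excess on DASH, or a real reduction that is hidden, could come from contact frequency. For symptoms the imbalance is more direct: the schedule shows a symptom instrument for one diet and none for the other.

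**Working it through.** The plan gives no figure on this point, so there is none to reproduce. The check sets the two phases side by side and then uses a simple capture model.

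**1. Routes by phase**

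| Route | DASH | SD |
|---|---|---|
| Interim event form at end of phase | yes | yes |
| Weekly dietitian call | yes | none described |
| Weekly food pick-up at the unit | yes | none described |
| Symptom and tolerance questionnaire | yes | no (marked DD only) |
| 24-hour phone line, visit reminders (SAP section 5) | yes | yes |

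Phase length is equal: "The duration of the intervention will be 4 weeks". Exposure time is therefore not a source of imbalance; capture is.

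**2. Capture model for flares**

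Assumptions, none given in the documents:
- q = share of flares captured on the end-of-phase form, the same on both diets
- s = share of the flares missed by the form that the calls recover, on DASH only

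Captured on SD: q. Captured on DASH: 1 − (1 − q)(1 − s). With a true ratio of 1, the apparent DASH:SD ratio is

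[1 − (1 − q)(1 − s)] / q

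Example, q = 0.8 and s = 0.25: [1 − 0.2 × 0.75] / 0.8 = 0.85 / 0.8 = 1.06.

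| q | s = 0 | s = 0.25 | s = 0.5 | s = 1 |
|---|---|---|---|---|
| 1.0 | 1.00 | 1.00 | 1.00 | 1.00 |
| 0.9 | 1.00 | 1.03 | 1.06 | 1.11 |
| 0.8 | 1.00 | 1.06 | 1.125 | 1.25 |
| 0.6 | 1.00 | 1.17 | 1.33 | 1.67 |

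In this model the ratio never falls below 1, so any distortion runs against DASH. At q = 0.8 and s = 1, a true 20% reduction would vanish: 0.8 × 1.25 = 1.0. At s = 0.25 it would shrink to 0.8 × 1.0625 = 0.85.

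**3. Effect on a test**

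Take 40 people per phase and an assumed 0.25 flares per person per phase, so 40 × 0.25 = 10 true flares on each diet. Let L1 and L0 be the expected captured counts on DASH and SD. Treating them as independent Poisson counts, with d = ln(L1/L0) / √(1/L1 + 1/L0), the two-sided 5% rejection rate is Φ(d − 1.96) + Φ(−d − 1.96).

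Example, q = 0.8 and s = 1: L1 = 10, L0 = 8, d = 0.223 / 0.474 = 0.47, rejection rate 0.076.

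Over s = 0.25 to 1:
- q = 0.9: 0.050 to 0.056
- q = 0.8: 0.052 to 0.076
- q = 0.6: 0.059 to 0.167

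If the flare rate is varied from 0.1 to 0.5 per person per phase, the highest value at q = 0.8 is 0.102 and at q = 0.6 is 0.288. These are normal approximations that ignore within-person pairing. They show order of magnitude only.

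**4. Form-only counting**

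Setting s = 0 gives a ratio of 1.00 at every q, provided q is the same on both diets.

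**5. Symptoms**

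The model does not apply. With the questionnaire given for DASH only, the schedule has no matching SD instrument. The descriptions of FP1 and FP2 in Protocol section 7 mention questions on adverse effects of the diet without limiting them to one diet. The table does limit them, so the two need to be aligned.

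**The case against.** **Call reports may never be counted.** No document says they are. Visits are the planned surveillance, and section 11 says only that reports on calls are possible. The schedule note says that grocery orders will be documented and mentions no event log. Protocol section 13 names case report forms, laboratory data and nutrient software as the main data sources. If flares come from the Interim event form alone, the calls add little or nothing. This stands, and it is why the point is a risk and not a demonstrated bias. It does not close the gap: SAP section 6 does not name that form, its content is not described, and no flare-specific instrument is scheduled at the end of either phase.

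**SD participants are not out of contact.** A 24-hour line and visit reminders are available in both phases, and section 11 provides continuous medical cover. This is true, but the line depends on the participant choosing to call, and reminders are not described as weekly.

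**Recall may be good.** Gout is very painful, and four weeks is short. If recall is complete, the ratio is 1.00. The documents do not settle this.

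**Form-only counting has its own bias.** Someone who flares on DASH, reports it on a call and misses the end-of-phase visit would drop out of the comparison. SAP section 5 anticipates study-related drop-out. This stands, and it calls for an all-source sensitivity analysis.

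**Stronger readings.** A reader might infer that the flare comparison is biased as planned, or that the ratio equals 1/q (1.11 at 90% recall, 1.25 at 80%). The documents support neither. The first needs call reports to be counted, which is not stated. The second needs grocery calls to recover every flare the form misses, and nothing says the dietitian asks about events. A reader might also extend the point to adverse events in general, but SAP section 6 compares only flares and self-reported symptoms.

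**Conclusion.** The point holds as an uncontrolled risk of differential ascertainment. The plan names a reporting route that exists on one diet only, schedules a symptom questionnaire on that diet only, and compares both outcomes between diets without equalizing the source. Any distortion from the extra reports would run against DASH.

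Its size is unknown and may be zero. With a true flare ratio of 1, the apparent ratio is 1.00 if visit recall is complete or the calls recover nothing, about 1.03 to 1.11 at 90% recall, and about 1.06 to 1.25 at 80%, where calls recover between a quarter and all of the missed flares. Recall, call yield and flare rate are all assumptions. At about 10 flares per phase, false-positive inflation is slight at 80 to 90% recall. The more practical problem is that one or two call-only reports could visibly move a ratio based on so few events.

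The symptom comparison is the weaker of the two: as scheduled, it has no like-for-like SD measurement. The primary analysis of serum uric acid is untouched.

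**What to change.** **In SAP section 6:**
- State that the main flare comparison uses only flares recorded on the Interim event form at FP1 and FP2, with identical questions and an onset date in both phases.
- List separately the flares reported only on calls or at pick-up.
- Add a sensitivity analysis that counts flares from all sources, including those of participants who miss the end-of-phase visit.

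**For symptoms:** ask the symptom items in both phases and align the section 7 table with the visit descriptions. Otherwise, report symptoms descriptively for DASH only and drop the comparison.

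**In Protocol section 11:** add a sentence saying that all reported events, from whatever source, still go to the study clinician, so safety review is unchanged.

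**Cost:** a few sentences in the two documents, one extra analysis, and a few questionnaire items at the end of the SD phase if the symptom comparison is kept. A few call-only flares leave the main comparison. Form-only counting may not equalize capture completely, because weekly contact on DASH could still prompt recall when the form is completed. That limitation should be stated with the result.

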12. ANALYSIS

The trial has sufficient resources to enroll 40 participants who will be randomly allocated to 1 of 2 sequences for each the two groups: (1) the SD group followed by the DD group or (2) the DD group followed by the SD group.

Power and sample size

Based on a cross-over trial design, using a variance of 1.71 at an alpha level of 0.05 with a power of 0.8, we estimated that we would need 41 participants to detect a change of -0.75 mg/dL between interventions.¹³ In two prior studies we had observed reductions of -1.3 and -1 mg/dL among subpopulations with a uric acid above 7 mg/dL.^{5,14}

Analysis Plan

This study is a randomized trial that tests the effects of an innovative intervention against a minimal intervention on a selected set of outcomes. The analysis will be conducted under the intent-to-treat principle for both the primary and the secondary endpoints. For the Primary Aim, groups will be compared using within-person differences in SUA levels. The analysis will be carried out with generalized estimating equations to compare 4-week SUA levels from both phases of the study, adjusted for baseline. This will allow us to test the null hypothesis that there is no difference in uric acid between the DASH diet intervention and the self-directed group (reference). Other outcome variables will be analyzed with a similar approach. For continuous outcomes, the distribution of outcome residuals will be assessed for normality and transformed where appropriate. Continuous outcomes will be analyzed via an identity function, while binary variables will be evaluated via a logit function.

Missing data

Based on the existing literature, we will employ recommended strategies to address missing data.⁷¹⁻⁷⁴ However, every effort will be made to collect outcome data on all participants.

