3.2 Power and sample size

Based on a cross-over trial design, using a variance of 1.71 at an alpha level of 0.05 using a twosided paired means test with a power of 0.8, we estimated that we would need 41 participants to detect a 4-week difference of -0.75 mg/dL between interventions.² In two prior studies we had observed reductions of -1.3 and -1 mg/dL among subpopulations with a uric acid above 7 mg/dL.^{3,4}

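### The stated 80% power at 41 participants does not describe the planned 40 with no allowance for lost pairs, and what power it should be depends on what 1.71 is

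*Protocol*

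**What the plan says.** The SAP's sample-size paragraph (section 3.2) states: "we estimated that we would need 41 participants to detect a 4-week difference of -0.75 mg/dL between interventions". Its inputs are given as "Based on a cross-over trial design, using a variance of 1.71" and "using a twosided paired means test with a power of 0.8". Protocol section 12 gives the same figures: "using a variance of 1.71 at an alpha level of 0.05" and "with a power of 0.8, we estimated that we would need 41 participants". Neither document says whether 1.71 belongs to the within-person difference or to a single measurement.

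On enrolment, the same protocol section opens with "The trial has sufficient resources to enroll 40 participants". The SAP introduction also gives 40. The protocol abstract sets 40 as a minimum, and the recruitment section gives it as an approximate target.

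On losses, SAP section 5 says "Reasons for any drop-outs will be documented". It plans imputation, best- and worst-case scenarios, and drop-out as an end-point if losses are related to the study. No drop-out rate and no inflation of the sample size appears in either document.

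**The concern.** A paired means test counts people with SUA at both follow-up visits, FP1 and FP2. That 41 means complete pairs is therefore inferred from the test named; the documents do not say so. A participant with one period only can stay in the generalized estimating equations model but adds little to a within-person contrast. The number of pairs is thus a fair guide to power.

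Read this way, the plan requires 41 pairs, enrols 40, expects that some participants may drop out, and still reports 80% power. What is at stake is interpretation. A non-significant result would be read against the only power statement in the documents, and that statement does not describe the trial as planned.

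**Working it through.** **Inputs.** Two-sided alpha 0.05, power 0.80, difference 0.75 mg/dL, paired test (SAP 3.2); 1.71 labelled as a variance (both documents); stated size 41; planned enrolment 40 (protocol 12, SAP introduction). Loss rates of 5, 10, 15 and 20% are my assumptions.

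**Step 1: reproduce 41.** With n pairs,

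n = (1.960 + 0.842)² × Var(difference) / 0.75², where (1.960 + 0.842)² = 7.849 and 0.75² = 0.5625.

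- 1.71 is the variance of the difference, as labelled: 7.849 × 1.71 / 0.5625 = 23.9, so 24 (paired t: 26).
- 1.71 is the within-person variance of one measurement, so Var(difference) = 2 × 1.71 = 3.42: 7.849 × 3.42 / 0.5625 = 47.7, so 48 (paired t: 50).
- 1.71 is the SD of the difference, so the variance is 1.71² = 2.924: 7.849 × 2.924 / 0.5625 = 40.8, so 41 (paired t: 43).

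Of these two-sided readings, only the third returns 41, and it does so by the normal approximation with no margin for loss. A one-sided test on the second reading comes close (38 normal, 39 to 40 by t), but the SAP specifies two-sided.

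**Step 2: the cost of 40 instead of 41, on the SD reading.**

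- Normal approximation: 80.2% to 79.2%.
- Paired t: 78.2% to 77.2%.

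Either way it is one point. Setting the t figure of 77% against the stated 80% would exaggerate the gap, because the 80% came from the normal formula.

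**Step 3: losses from 40 enrolled.** Paired-t power for 0.75 mg/dL, from the noncentral t with n - 1 degrees of freedom and noncentrality 0.75 × √n / SD of the difference:

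| Complete pairs (assumed loss) | SD of difference 1.71 | Variance of difference 1.71 | Per-measurement variance 1.71 |
|---|---|---|---|
| 40 (0%) | 77.2% | 94.3% | 70.6% |
| 38 (5%) | 75.0% | 93.1% | 68.3% |
| 36 (10%) | 72.5% | 91.7% | 65.8% |
| 34 (15%) | 69.9% | 90.1% | 63.1% |
| 32 (20%) | 67.1% | 88.1% | 60.4% |

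**Step 4: difference detectable with 80% power, SD reading, same t basis.** Solving the same power function for the difference gives about 0.78 mg/dL at 40 pairs, and 0.80, 0.82, 0.85 and 0.87 mg/dL at 38, 36, 34 and 32 pairs.

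**The case against.** The strongest reply is that both documents call 1.71 a variance. Taken as the variance of the paired difference, 26 pairs suffice by paired t (80.3%), so 14 of the 40 could be lost before power fell below 80%. A reader might infer from the missing drop-out allowance that the trial is underpowered. The documents do not support that as a flat statement. It holds on the SD and per-measurement readings and fails on the label as written. The label as written, however, contradicts the 41 printed beside it, so it does not rescue the statement.

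Other points against:

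- *One participant is trivial.* This stands; the gap of one is worth about one point.
- *The loss rates are not in the documents.* This also stands. The documents list retention measures and plan data collection even after a participant stops the intervention. The two post-randomisation periods last only 4 weeks each, with no washout. Losses may be small.
- *The abstract's minimum of 40 leaves room for more.* It does, so 41 pairs are not ruled out. But protocol section 12 ties 40 to resources, and the timeline's 1 to 2 patients per month over about 15 months gives only 15 to 30.
- *Uric acid may not be marked missing (protocol section 13).* That is a data-entry rule and does not retain anyone.
- *The prior reductions cited are larger, -1.0 and -1.3 mg/dL.* This limits the consequence. At 1.0 mg/dL, 32 pairs with an SD of 1.71 still give 89% by paired t.

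**Conclusion.** The point holds as a mismatch between the stated size and power and the planned trial. None of the three two-sided readings of 1.71 makes 80% the right figure for 40 enrolled with some pairs lost: power is lower on two readings and higher on one. On the reading that reproduces 41, the missing participant matters little and the absent loss allowance matters more: about 77% with no loss, and 75 to 67% with 5 to 20% lost. These figures rest on assumed loss rates and on the pair count as a guide to the planned model.

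A reader might go further and conclude that the design cannot deliver 80% power, or write about 70 to 75% into the plan outright. That is not supported. If the label is right, power at 34 to 38 pairs is 90 to 93%, and such text would be wrong by about 20 points. The meaning of 1.71 has to be settled first. The consequence is confined to how a null result at -0.75 mg/dL is read; the analysis and conduct are unaffected.

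**What to change.** No further enrolment is needed. In protocol section 12 and SAP section 3.2:

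1. State whether 1.71 is an SD or a variance, and of what: the within-person difference or a single measurement.
2. Replace the statement of 41 participants at 0.8 with power and detectable difference for 40 randomised and for a stated, assumed number of complete pairs, using the paired t throughout.

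If the SD reading is confirmed, suitable text would be:

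> 40 will be randomised; power for -0.75 mg/dL is about 77% with 40 complete pairs and about 70-75% with 34-38, and 80% power applies to differences of about -0.80 to -0.85 mg/dL with 34-38 pairs.

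If another reading is confirmed, take the figures from the matching column of the table. The cost is a sentence or two in each document. On the SD reading, the stated power becomes less favourable.
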